### Panel 6: Combinations of IMP administration per dose regimen

	LEO 138559, █ mg/mL	Placebo
Dose regimen 1		
LEO 138559 █ mg	2 x 2 mL	1 x 1 mL
Dose regimen 2		
LEO 138559 █ mg	1 x 2 mL 1 x 1 mL	1 x 2 mL
Dose regimen 3		
LEO 138559 █ mg (loading dose)	2 x 2 mL	1 x 1 mL
LEO 138559 █ mg	1 x 2 mL	1 x 2 mL 1 x 1 mL
Dose regimen 4		
LEO 138559 █ mg (loading dose)	1 x 2 mL	1 x 2 mL 1 x 1 mL
LEO 138559 █ mg	1 x 1 mL	2 x 2 mL
Placebo regimen		
Placebo	-	2 x 2 mL 1 x 1 mL

**Note:** Placebo administrations to mask the weekly loading doses will be identical to the administrations in the placebo regimen.

During the treatment period, final dosing will be administered at Week 14 and only clinical assessment will occur at Week 16. IMP administration will continue until Week 14.

IMP will be administered by qualified, unblinded site staff as the active drug is visually distinct from placebo (see [Section 6.3.2](#) for blinding details). The IMP must be injected SC in the upper legs (thighs), stomach area (abdomen) or in the upper, outer arm but should not be given into areas where the skin is tender, bruised, red, hard, thick, scaly, or affected by AD. It is advised that the site of injection of IMP is rotated such that the subject receives IMP at a different anatomical part (i.e. anterior thigh, abdomen or upper arm) at each treatment visit. The anatomical location of the injection (left/right anterior thigh, left/right abdominal region, left/right upper arm) must be recorded in the source documents at each treatment visit and recorded in the eCRF.

At each treatment visit, the 3 injections of IMP must be administered within a maximum of 10 minutes. The 3 injections of IMP should be administered in the same injection site area (e.g. left upper arm) separated by at least 3 cm.

If any issues with the IMP (e.g. damaged kit or vial/syringe) or a malfunction during administration should arise, the unblinded CRA should be contacted, and the issue should be documented.

Further details on IMP preparation and administration will be provided in an instruction for use and in the trial product handling manual. IMP administration must be carried out according to these instructions.

### **After IMP administration**

At Weeks 0, 1, 2, 3, and 4, subjects will be monitored for potential immediate drug reactions for a minimum of 2 hours after IMP administration. Vital signs will be taken immediately (within 5 minutes) after last IMP administration, as well as after 30 minutes ( $\pm$  5 minutes), after 1 hour ( $\pm$  5 minutes), and after 2 hours ( $\pm$  5 minutes), or until stable, whichever is later **(for requirements specific for EU countries i.e. CZ, DE, ES, FR, HU, PL and RO, see Section 12.5.1)**. Vital signs will be documented in the eCRF.

As with any Ab, allergic reactions to dose administration are possible. The World Allergy Organization has categorized anaphylaxis into 2 subgroups: allergic anaphylaxis (mediated by an immunologic mechanism) and nonallergic anaphylaxis (which has a nonimmunologic cause) (64). The clinical criteria for defining anaphylaxis for this trial are listed in Appendix 4 (Section 12.4) and (65). Appropriate drugs, such as epinephrine, antihistamines, corticosteroids, etc., and medical equipment to treat acute anaphylactic reactions must be immediately available at trial sites, and trial personnel should be trained to recognize and respond to anaphylaxis according to local guidelines.

If an anaphylactic reaction occurs, a blood sample will be drawn from the subject 1) as soon as possible after the event, 2) at 60 minutes ( $\pm$  30 minutes) after the event, and 3) at discharge for analysis of serum tryptase at the central laboratory.

### **Conditions requiring IMP administration rescheduling**

If any of the following should occur, the investigator should reschedule the visit and IMP should not be administered until the rescheduled visit:

- The subject has an intercurrent illness that in the opinion of the investigator may compromise the safety of the subject in the trial.

THIS DOCUMENT CONTAINS CONFIDENTIAL INFORMATION AND MUST NOT BE COPIED OR MADE AVAILABLE TO ANY THIRD PARTY WITHOUT THE PRIOR WRITTEN CONSENT OF THE LEO PHARMA GROUP

- The subject is febrile (defined as  $\geq 38^{\circ}\text{C}$ ;  $\geq 100.4^{\circ}\text{F}$ ) within 72 hours prior to IMP administration.

From baseline to Week 4, if the trial visit cannot be rescheduled in order to maintain a minimum of 5 days to subsequent dose, the sponsor's medical expert should be contacted. From Week 4 and onwards, if the trial visit cannot be rescheduled in order to maintain a minimum of 7 days to subsequent dose, the sponsor's medical expert should be contacted.

Overdose is specified in Section 10.7.2. LEO Pharma does not have any specific treatment recommendations in relation to overdose. The investigator will use clinical judgement to treat any overdose if necessary.

## 6.3 Treatment assignment and blinding

### 6.3.1 Treatment assignment

Subjects who meet all the eligibility criteria (Sections 5.1 to 5.3) will be randomized at baseline (Day 1) to receive treatment according to 1 of the treatment regimens outlined in Section 6.2.

Treatment assignment will be pre-planned according to a computer-generated randomization schedule in a 1:1:1:1:1 ratio (4 LEO 138559 dose regimens and 1 placebo regimen), based on a permuted block design and stratified by baseline disease severity (baseline vIGA-AD score), region (Japan, Other countries), prior use of biologics or systemic JAK inhibitors for AD (Yes/No), and baseline biopsy status (willingness to provide biopsies: Yes/No).

IRT will be used to control randomization and stratification factors, along with IMP supply chain, and expiry tracking.

### 6.3.2 Blinding

This is a double-blinded trial in which LEO 138559 and placebo are visually distinct from each other and not matched for viscosity. Neither the subject nor any of the investigators or LEO Pharma staff (except unblinded LEO team members, such as the unblinded CRA, unblinded GCTM, or unblinded CPM, etc.) who are involved in the clinical evaluation and monitoring of the subjects will be aware of the treatment received.

IMP will be prepared, handled, and administered by qualified, unblinded site staff who will not be involved in the management of trial subjects and who will not perform any of the assessments.

THIS DOCUMENT CONTAINS CONFIDENTIAL INFORMATION AND MUST NOT BE COPIED OR MADE AVAILABLE TO ANY THIRD PARTY WITHOUT THE PRIOR WRITTEN CONSENT OF THE LEO PHARMA GROUP

In the event that the treatment allocation for a subject becomes known to the investigator, other trial staff involved in the management of trial subjects, or a trial subject, LEO Pharma must be notified immediately.

Should an issue arise with the IMP (e.g. damaged kit or syringe that has been assigned to a subject prior to administration, or any other unexpected event with the kit or syringe [e.g. a malfunction during IMP administration]), the unblinded site staff will contact the unblinded CRA to determine whether any specific actions are required.

The trial site will maintain a written plan (site blinding plan) detailing which staff members are blinded/unblinded and the process of IMP administration used to maintain the blind.

### **6.3.3 Emergency unblinding of individual subject treatment**

While the safety of a subject always comes first, it is still important to carefully consider if unblinding is necessary to ensure a subject's safety. An emergency unblinding request can be made by the investigators, HCPs who are not members of the trial staff, or authorized LEO Pharma personnel.

Provisions are in place for 24-hour emergency unblinding of individual subject treatment. If emergency unblinding is required, the investigator can unblind a subject's treatment via the IRT system, or unblinding CRO. Only the investigator should be unblinded and keep treatment allocation confidential. LEO Pharma must remain blinded until the end of the trial.

For a requester who is not a member of the trial staff and who does not have access to the IRT system (e.g. a physician at an emergency room), a local contact number for the emergency unblinding CRO is provided on the subject card (see Appendix 1 [Section 12.1.3]) to be used if the investigator or delegated site staff cannot be reached. The requester will provide the trial ID and subject ID to the emergency unblinding CRO who will immediately reveal the individual treatment allocation.

The emergency unblinding CRO will clarify that the requester requires immediate unblinding without further medical consultation. Should the requester wish to discuss whether unblinding is necessary, the emergency unblinding CRO will provide the requester with the LEO Pharma 24/7 medical cover.

LEO Pharma Global Safety may unblind subject(s) if it is deemed necessary, including for regulatory purposes in relation to reporting of SUSARs.

THIS DOCUMENT CONTAINS CONFIDENTIAL INFORMATION AND MUST NOT BE COPIED OR MADE AVAILABLE TO ANY THIRD PARTY WITHOUT THE PRIOR WRITTEN CONSENT OF THE LEO PHARMA GROUP

## 6.4 Background treatment

All subjects should continue using their current daily skin care moisturizing routine from screening throughout the trial (until Week 32), if approved by the investigator, who will otherwise make an alternative suggestion.

## 6.5 Rescue treatment

Rescue treatment is defined as the use of any of the prohibited medications or procedures listed in no. 1-6 of Section 6.7 initiated to treat intolerable AD signs and/or symptoms during the treatment and follow-up period. Rescue treatment for AD may be prescribed to trial subjects at the discretion of the investigator.

- In case rescue treatment is initiated before Week 4:
  - IMP will be permanently discontinued (see Section 7.2.1).
- In case rescue treatment is initiated at or after Week 4:
  - Subjects should preferably be started on topical treatment (TCS and/or TCI), and these subjects will continue IMP and the schedule of trial visits and assessments. Rescue treatment should only be used in situations where the subject is at risk of discontinuation, and should be continued for as short a period as possible.

*Note: It is recommended that the investigator starts with a TCI or least potent TCS for the face (e.g. hydrocortisone 1%, 2.5% cream/ointment) and moderately potent TCS for the body (e.g. triamcinolone acetonide 0.1% cream/ointment).*

- If the subject experiences intolerable AD signs and/or symptoms and the TCS and/or TCI rescue treatment is insufficient, the subject might need to progress to other rescue treatment or procedures listed in Section 6.7. In that case, IMP will be permanently discontinued (see Section 7.2.1).
- In case rescue treatment is initiated at or after Week 16:
  - If the subject experiences intolerable AD signs and/or symptoms during the follow-up period (Week 16 to 32), topical and systemic rescue treatment or procedures listed in Section 6.7 may be prescribed at the discretion of the investigator. In such case, subjects will continue the schedule of trial visits and assessments.

Investigators should make every attempt to conduct efficacy and safety assessments (for example disease severity scores, safety laboratory assessments) immediately before administering rescue treatment. An unscheduled visit may be used for this purpose, if necessary.

### Reporting in eCRF

It will be recorded in the eCRF if a medication or procedure is given as rescue treatment.

THIS DOCUMENT CONTAINS CONFIDENTIAL INFORMATION AND MUST NOT BE COPIED OR MADE AVAILABLE TO ANY THIRD PARTY WITHOUT THE PRIOR WRITTEN CONSENT OF THE LEO PHARMA GROUP

## 6.6 Prior and concomitant medication and concurrent procedures

Any medication or vaccine that the subject receives from 3 months (12 months for medications related to AD) prior to screening through the follow-up period must be recorded in the subject's medical record and the eCRF along with details such as:

- Medication name or therapy (generic or brand name).
- Whether the medication or therapy is a rescue treatment for AD.
- Indication.
- Start and stop date of administration (it will also be recorded if the medication is ongoing).
- Dose information, including dose per administration, unit, and frequency.
- Route of administration.

Similarly, any concurrent procedure conducted within 3 months prior to screening through the follow-up period must also be recorded in the subject's medical record and the eCRF with details such as:

- Procedure name (include anatomical area if relevant).
- Indication.
- Start and stop date (it will also be recorded if the procedure is ongoing).

Investigators may prescribe concomitant medications or procedures to provide adequate supportive care as deemed necessary, except for treatments listed in Section 6.7. The sponsor's medical expert should be contacted if there are any questions regarding concomitant or prior medications and procedures.

The following concomitant medications are permitted during the trial:

- Paracetamol use (maximum 2 g/day).
- Concomitant therapies taken for the long-term treatment of pre-existing conditions can continue during the trial provided they are not violating the exclusion criteria (see Section 5.3) and the list of prohibited medications (Section 6.7).
- Systemic antihistamines and/or anti-infectives.
- Ophthalmic, inhaled, and nasal corticosteroids.

## 6.7 Prohibited medications and procedures

The medications and procedures listed below are prohibited during the trial from randomization (Week 0). Medications and procedures disallowed prior to randomization are covered by the exclusion criteria (see Section 5.3). In case any prohibited treatments are used during the trial, they must be recorded in the eCRF as concomitant medication.

THIS DOCUMENT CONTAINS CONFIDENTIAL INFORMATION AND MUST NOT BE COPIED OR MADE AVAILABLE TO ANY THIRD PARTY WITHOUT THE PRIOR WRITTEN CONSENT OF THE LEO PHARMA GROUP

From randomization through the last follow-up visit (Week 32), the below treatments are prohibited:

1. TCS and TCI.
2. Topical PDE-4 inhibitors.
3. Topical JAK inhibitors.
4. Use of UVA or UVB, PUVA, other phototherapy, tanning beds, or prolonged sun exposure.
5. Systemic corticosteroids (nasal, ophthalmic, and inhaled corticosteroids are allowed).
6. Systemic treatment with immunosuppressive drugs (e.g. methotrexate, cyclosporine, azathioprine), immunomodulating drugs, JAK inhibitors, and retinoids (e.g. alitretinoin).
7. Biological products.
8. Investigational agents other than LEO 138559.
9. Allergen immunotherapy.
10. Live (attenuated) vaccine.
11. Immunoglobulins.
12. Blood products.

Prescription of prohibited medications and procedures in no. 1-6 do not constitute a protocol deviation if given as rescue treatment for AD (Section [6.5](#)). If prohibited medications and procedures are used for reasons other than rescue treatment for AD, they must be recorded as protocol deviations and IMP will be permanently discontinued (see Section [7.2.1](#)).

Please note that receipt of inactive/killed vaccines (e.g. inactive influenza) is allowed, provided that they are not administered within 5 days before/after any trial visit.

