#### Screening period (between 0 and 4 weeks prior to the baseline visit [Day 1])

Eligibility of the subject ([Sections 5.1](#) to [5.3](#)) to participate in the trial will be evaluated at a screening visit (Visit 1) and at the baseline visit (Visit 3). The screening visit will be performed up to 4 weeks before the baseline visit (Visit 3).

Moreover, at the screening visit (Visit 1), the subjects will receive training in completion of an eDiary and will be given an electronic device to record the ADSD, Nocturnal [REDACTED], Difficulty [REDACTED], and Frequency of [REDACTED] During the Night. Completion of the eDiary twice daily will be initiated at the latest 1 week prior to the baseline visit (Visit 3, Week 0).

At the start of the washout period (from Visit 2, Week -1), subjects should stop any treatment with TCS, TCI, topical PDE-4 inhibitors, topical JAK inhibitors, or other medicated topical treatments.

THIS DOCUMENT CONTAINS CONFIDENTIAL INFORMATION AND MUST NOT BE COPIED OR MADE AVAILABLE TO ANY THIRD PARTY WITHOUT THE PRIOR WRITTEN CONSENT OF THE LEO PHARMA GROUP

Subjects should continue using their current daily skin care moisturizing routine from screening throughout the trial (until Week 32), if approved by the investigator, who will otherwise make an alternative suggestion.

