#### Prior/concomitant therapy

18. Previous treatment with LEO 138559.
19. Previous exposure to fezakinumab (anti-IL-22 Ab).
20. Systemic treatment with immunosuppressive drugs (e.g. methotrexate, cyclosporine, azathioprine), immunomodulating drugs, retinoids (e.g. alitretinoin), corticosteroids (steroid eyedrops and inhaled or intranasal steroids are allowed), or JAK inhibitors within 28 days or 5 half-lives prior to baseline, whichever is longer.
21. Use of tanning beds or phototherapy (NBUVB, UVB, UVA1, PUVA), within 4 weeks prior to baseline.
22. Receipt of blood products within 28 days prior to screening.
23. Treatment with:
  - Any marketed or investigational biologic agents within 3 months or 5 half-lives, whichever is longer, prior to baseline.

THIS DOCUMENT CONTAINS CONFIDENTIAL INFORMATION AND MUST NOT BE COPIED OR MADE AVAILABLE TO ANY THIRD PARTY WITHOUT THE PRIOR WRITTEN CONSENT OF THE LEO PHARMA GROUP

- Any cell-depleting agents including but not limited to rituximab: within 6 months prior to baseline, or until lymphocyte count returns to normal, whichever is longer.

24. Treatment with TCS, TCI, topical PDE-4 inhibitors, topical JAK inhibitors, or other medicated topical treatments within 7 days prior to baseline. *NOTE: Subject may be rescreened (once) if failed for this criterion. However, rescreening will require approval by the sponsor's medical expert (see Section 5.4).*

25. Receipt of live attenuated vaccines 30 days prior to baseline or longer if recommended so by local guidelines.

26. Treatment with any non-marketed drug substance (that is, an agent which has not yet been made available for clinical use following registration) within the last 4 weeks or 5 half-lives prior to randomization, whichever is longer.

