## 9 Scientific rationale for trial design and appropriateness of assessments

### 9.1 Scientific rationale for trial design

This is a randomized, double-blind, placebo-controlled, multi-site, parallel-group, dose-finding trial, which will be conducted in accordance with the protocol, ICH GCP, and applicable regulatory requirements.

The trial will be conducted at multiple trial sites located in Europe, North America, and Japan.

Patients with AD represent a heterogeneous patient population with disease severity ranging from mild to severe. To mitigate any potential difference in trial outcome based on baseline characteristics, eligibility criteria for inclusion have been carefully selected and trial subjects will be randomized according to a stratified, permuted block design. The randomization will minimize selection bias and ensure that the effect of treatment is not confounded by baseline factors. The stratified permuted block design and the inclusion of prognostic baseline factors in the analysis will improve the precision of the estimated treatment effect.

The most important inclusion criteria for entry into the trial is a diagnosis of AD (as defined at screening by the Hanifin and Rajka 1980 criteria (62)) and history of AD for at least 1 year, to ensure correct diagnosis and rule out differential diagnoses.

Patients with moderate-to-severe AD with inadequate response to treatment with TCS ( $\pm$ TCI as appropriate), or for whom these topical AD treatments are medically inadvisable, are the target population for treatment with LEO 138559. Only adults (aged 18–75 years) are included. In order to evaluate any efficacy of LEO 138559, subjects in the trial cannot be on concomitant medication for AD or have diseases that may influence the evaluation of AD signs and symptoms.

LEO Pharma plans to evaluate LEO 138559 administered SC in 4 different dose regimens.

The following LEO 138559 dose regimens will be included:

- Dose regimen 1: LEO 138559 [REDACTED] mg SC Weeks 0, 1, 2, 3 and then [REDACTED] mg SC Q2W from Week 4.
- Dose regimen 2: LEO 138559 [REDACTED] mg SC Weeks 0, 1, 2 and then [REDACTED] mg SC Q2W from Week 4.
- Dose regimen 3: LEO 138559 [REDACTED] mg SC Weeks 0 and 2 and then [REDACTED] mg SC Q2W from Week 4.
- Dose regimen 4: LEO 138559 [REDACTED] mg SC Weeks 0 and 2 and then [REDACTED] mg SC Q2W from Week 4.

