### Description of intercurrent events

An intercurrent event refers to a post-baseline event that affects either the interpretation or the existence of the measurements of an endpoint. For the purposes of this trial, we define the following 2 intercurrent events:

- ***Initiation of rescue treatment:*** This event occurs when a subject initiates rescue treatment as listed in no. 1-6 of Section 6.7 for intolerable AD signs and/or symptoms. The timing of the event will be taken as the date of initiation of the rescue treatment recorded in the eCRF.
- ***Permanent discontinuation of IMP:*** This event occurs when a subject permanently discontinues IMP. This event can occur either at the subject's own initiative or at the investigator's or sponsor's discretion. The timing of the event will be taken as the date of permanent discontinuation of IMP as recorded in the eCRF.

[Panel 16](#) provides an overview of the estimand strategies defined in Sections 11.3.7.1, 11.3.7.2, and 11.3.7.3 that will be used to address occurrences of the intercurrent events described above.

An overview of statistical analysis of endpoints can be found in [Panel 17](#).

THIS DOCUMENT CONTAINS CONFIDENTIAL INFORMATION AND MUST NOT BE COPIED OR MADE AVAILABLE TO ANY THIRD PARTY WITHOUT THE PRIOR WRITTEN CONSENT OF THE LEO PHARMA GROUP

**Panel 16: Handling of observed and missing data according to intercurrent events in the primary analysis of the estimands defined in Sections 11.3.7.1, 11.3.7.2, and 11.3.7.3**

Events	Observed data or missing	Continuous endpoints			Binary endpoints		TTE endpoints
		Primary Estimand	Hypothetical Suppl. Estimand	Second Suppl. Estimand	Primary Estimand	Suppl. Estimand	
Initiation of rescue treatment	Observed	Treated as missing, MI	Treated as missing, MI	Value will be used as observed	NRI	Value will be used as observed	Not applicable
	Missing	MI	MI	MI	NRI	MI	Not applicable
Permanent discontinuation of IMP, for reasons other than lack of efficacy or an AE related to worsening of AD	Observed	Treated as missing, MI	Treated as missing, MI	Value will be used as observed	Treated as missing, MI	Value will be used as observed	Accounted for as a competing risk a
	Missing	MI	MI	MI	MI	MI	Accounted for as a competing risk a

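### Medicated topicals outside the four named classes are stopped before baseline, but the documents conflict on them after randomization and no intercurrent-event rule covers their use

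*Combined protocol and SAP*

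**What the plan says.** Before baseline, the rule covers five topical groups. Section 4.1 says that from the start of washout "subjects should stop any treatment with TCS, TCI, topical PDE-4 inhibitors, topical JAK inhibitors, or other medicated topical treatments". Exclusion criterion 24 in Section 5.3, repeated for EU countries in Section 12.5.1.2, excludes "Treatment with TCS, TCI, topical PDE-4 inhibitors, topical JAK inhibitors, or other medicated topical treatments within 7 days prior to baseline".

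After randomization, Section 6.7 governs: "From randomization through the last follow-up visit (Week 32), the below treatments are prohibited". Items 1-3 are the four named topical classes, item 4 is phototherapy and sun exposure, items 5-6 are systemic, and items 7-12 are biologics, other investigational agents, immunotherapy, live vaccines, immunoglobulins and blood products. The fifth topical group is in none of them. Section 6.7 also assigns restrictions before randomization to the exclusion criteria.

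Two other sections bear on the same use. Section 6.6 says "Investigators may prescribe concomitant medications or procedures to provide adequate supportive care as deemed necessary, except for treatments listed in Section 6.7", and lets long-term treatment of existing conditions continue only if it breaks neither the exclusion criteria nor Section 6.7. Section 9.1 says that "subjects in the trial cannot be on concomitant medication for AD".

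The analysis definitions follow the Section 6.7 numbering. Section 6.5: "Rescue treatment is defined as the use of any of the prohibited medications or procedures listed in no. 1-6 of Section 6.7". Section 11.3.7: "This event occurs when a subject initiates rescue treatment as listed in no. 1-6 of Section 6.7". The only other intercurrent event is permanent discontinuation of IMP. Section 11.3.8.1 removes data only after one of these two events, and Panel 16 uses the observed value when neither has occurred.

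**The concern.** Baseline EASI is measured off all five topical groups. The primary estimand describes a setting in which rescue is not available and IMP is not stopped. A medicated topical outside the list, started for AD after randomization, would work against that setting much as a listed one does, but nothing in the analysis rules responds to it. Two subjects who each start a topical for intolerable AD could then be handled in opposite ways, depending only on whether the product falls in one of the four named classes. If such use were more common on placebo, the placebo response would be improved by it and the difference between each regimen and placebo would shrink.

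**Working it through.** **Setting the rules side by side**

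| Rule | Listed topical (items 1-3) started for intolerable AD | Medicated topical outside the list, same reason |
|---|---|---|
| Stopped for 7 days before baseline (5.3, no. 24) | Yes | Yes |
| Named as prohibited from Week 0 (6.7) | Yes | No |
| Rescue (6.5) | Yes | No |
| Mandatory end of IMP (7.2.1) | Yes, except TCS/TCI rescue at or after Week 4 | No; investigator discretion only |
| Intercurrent event (11.3.7) | Yes | No |
| Later EASI in primary analysis (11.3.8.1, Panel 16) | Treated as missing and imputed | Used as observed |
| Binary endpoints (11.3.8.2) | Non-responder | Responder if the threshold is met |

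Five groups are washed out and four carry over into Section 6.7 and the rescue definition: 5 - 4 = 1 missing from both.

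**How much it could matter**

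The plan gives no figure for such use. To see which comparison is most exposed, I first reproduce the plan's power for regimen 4 versus placebo.

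- Inputs: Week 16 mean changes of -10.0 and -3.5 (Panel 14); variance 111.0, 50 subjects per arm, and 40% withdrawing or with an intercurrent event in both arms (Section 11.1); two-sided 5% (Section 11.3.1).
- Effective n per arm = 50 x (1 - 0.40) = 30.
- SE = sqrt(111.0 x 2/30) = 2.72 EASI points.
- Power = Phi(6.5/2.72 - 1.96) = Phi(0.43) = 66.6%, against 67.4% in Panel 15.

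The same formula gives 97.6% for regimen 3 and 99.6% for regimen 2 (Panel 15: 97.2% and 99.1%). It works on absolute change and ignores the bounding of EASI. It does not reproduce regimen 1 versus 2 (63.0% against 49.7%), which is not used here.

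Dilution = (share of users on placebo - share on active) x extra EASI reduction from the topical. **The shares and effects below are assumptions, not figures from the documents.**

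| Placebo share | Active share | Effect (EASI points) | Dilution | Regimen 4 power |
|---|---|---|---|---|
| 5% | 0% | 3 | 0.05 x 3 = 0.15 | Phi(6.35/2.72 - 1.96) = 64.6% |
| 30% | 0% | 6 | 0.30 x 6 = 1.8 | Phi(4.70/2.72 - 1.96) = 40.8% |
| 5% | 2.5% | 3 | 0.025 x 3 = 0.075 | 65.6% |
| 30% | 15% | 6 | 0.15 x 6 = 0.9 | 53.9% |

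At the second row's extreme, regimen 3 falls to 90.0%, regimen 2 to 97.6%, and regimen 1 stays at about 100%. Equal use with equal effect in both arms gives no dilution, and more use on active would move the difference away from the null.

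**The case against.** A reader might infer that the plan lets subjects restart these topicals on Day 1, because Section 6.6 permits whatever Section 6.7 omits. The documents do not support that. Section 9.1 rules out concomitant AD medication. Section 4.1 tells subjects to stop and names no point at which they may resume. Section 6.6 limits prescribing to supportive care, ties continuing long-term therapies to the exclusion criteria, and refers questions to the sponsor's medical expert. This is conflicting text, not permission.

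That defeats the stronger reading but leaves the analysis gap. Section 9.1 is rationale and attaches no deviation, discontinuation or analysis consequence. Criterion 24 looks back 7 days from baseline, so a new prescription afterwards does not breach it.

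It can also be said that use will be rare. The residual class is narrow, no agent in it is named, and from Week 4 a subject doing poorly can have TCS or TCI rescue, a defined intercurrent event, and stay on IMP. This stands as a reason to expect a small effect. It is weaker before Week 4, when any rescue ends IMP.

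Nor would use be invisible: Section 6.6 records product, indication and dates, and Section 11.3.1 provides for a blinded review before the SAP is final. That is right, and it makes the remedy cheap, but I found no rule saying what to do with the record.

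Finally, if the clinical team decided to allow these topicals, handling their use like rescue would extend the estimand, which at present removes only rescue and IMP discontinuation. That also stands. The event should be named openly in Section 11.3.7, not absorbed through interpretation.

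**Conclusion.** The point holds as an inconsistency with an analysis consequence. The documents disagree on whether medicated topicals outside the four named classes may be used for AD after randomization. Whatever the answer, no intercurrent-event rule covers that use, so the stated rules would treat it differently from the same use of a listed topical.

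A reader might go further and conclude that the regimen-versus-placebo results will be materially diluted. The documents give neither a usage rate nor an effect, so the size is unknown. The range above is illustrative: its lower end is negligible, and its upper end assumes a topical effect of 6 points, close to the whole 6.5-point difference assumed for regimen 4. What can be said is conditional: the bias is toward the null if use is more common on placebo, and regimen 4 has the least power to spare. This is worth correcting before unblinding; it does not threaten the design.

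**What to change.** 1. Reconcile Sections 4.1, 5.3 (no. 24), 6.5, 6.6, 6.7 and 9.1 so that they say the same thing about these topicals before and after randomization. Which clinical rule applies is for the clinical team.
2. Settle how values after rescue are imputed in the primary continuous analysis. Panel 16 says multiple imputation; Section 11.3.8.1 puts rescue in the group imputed by last observation carried forward. Until this is resolved, handling something like rescue has no single meaning.
3. Before unblinding, state in Section 11.3.7 or the SAP that starting another medicated topical for AD after randomization is handled in the same way as initiation of rescue treatment, for continuous and binary endpoints. Identify it from the indication and start date already recorded under Section 6.6, during the blinded review in Section 11.3.1.

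The cost is a few sentences and a blinded check of concomitant medication; no new data are collected, and the planned sample size and alpha are unchanged. The downside is that some additional observed values become missing or non-response. If use were rare, this would be few subjects; at an assumed 20% of a 50-subject arm it would be 10, so the number affected per arm should be reported.
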